9.1. Demographic and Other Baseline Characteristics

Sex, ethnicity, and race of all subjects will be summarized by sequence ([Table 9](#)). Ethnicity will be categorized as “Hispanic or Latino,” “Not Hispanic or Latino,” “Unknown,” or “Not Reported.” In accordance with NIH reporting policy, subjects may self-designate as belonging to more than one race or may refuse to identify a race, the latter reflected in the case report form (CRF) as “No” to each racial option. Age, height, weight, and BMI will be summarized by sequence ([Table 10](#)).

Individual subject listings will be presented for all demographic and baseline characteristics ([Listing 5](#)). Note that while weight may be measured once prior to the first dose, the height, weight, and BMI from the first screening visit will be considered the baseline values.

9.1.1. Prior and Concurrent Medical Conditions

All current illnesses and past pre-existing medical conditions will be coded using MedDRA dictionary version 20.1 or higher. Summaries of subjects’ pre-existing medical conditions by MedDRA system organ class (SOC) will be presented by sequence and overall ([Table 11](#)). Individual subject listings will be presented for all medical conditions ([Listing 6](#)).

9.1.2. Prior and Concomitant Medications

All medications will be coded using the current version of the World Health Organization (WHO) Drug dictionary (WHO Drug Dictionary Enhanced C3 September 1, 2018 or higher). The use of prior and concomitant medications taken during the study will be summarized by treatment and by Anatomical Therapeutic Code ATC 1 and ATC 2 (separately in [Table 30](#) for prior medications and [Table 31](#) for

concomitant medications). Individual subject listings will be presented for all prior and concomitant medications (separately in [Listing 19](#) for prior medications and [Listing 20](#) for concomitant medications).

Drugs will be listed and summarized as prior medications when the end date for the medication is before the first dose of study product and listed and summarized as concomitant medications otherwise.

9.2. Measurements of Treatment Compliance

Date and time of each treatment will be included in [Listing 7](#).

9.3. Adverse Events

When calculating the incidence of AEs (i.e., on a per subject basis) within a given AE class (MedDRA category), each subject will only be counted once for each treatment and any repetitions of AEs within a subject/treatment will be ignored. For each treatment received, the worst severity observed for the subject within the observation period and AE class will be reported. The denominators for percent values will be indicated within the table or table header and denominators will consist of the maximal size of the safety population in the indicated observation period.

9.3.1. Unsolicited Adverse Events

A brief overall summary of AEs by treatment will be shown ([Table 12](#)), including number of subjects with at least 1 AE of any severity, number of subjects with at least 1 related AE of any severity, and number of subjects with at least 1 SAE.

AEs by subject will be presented in [Listing 8](#). A subject listing of non-serious AEs of moderate or greater severity will be reported ([Table 16](#)).

The following summaries for unsolicited AEs will be presented:

- Tabularly, the total number of AEs and the number and proportion of subjects reporting at least one unsolicited AE, summarized by treatment, MedDRA SOC, HLGT, and PT ([Table 13](#)). Denominators for percentages are the number of subjects who received the treatment being summarized. 95% CIs (Wilson CIs) will be presented for proportions.
- Tabularly, the number and proportion of subjects reporting at least one unsolicited AE, summarized by treatment, SOC, HLGT, PT, severity, and relatedness ([Table 14](#)).
- Graphically, by treatment, bar charts of frequency of related serious and non-serious AEs by severity and MedDRA SOC (and overall for any SOC) ([Figure 3](#), [Figure 4](#), [Figure 5](#), [Figure 6](#), [Figure 7](#)). These figures describe the total number of occurrences of each event, including multiple occurrences per subject.
- Graphically, by treatment, bar chart of incidence of related serious and non-serious AEs by severity and MedDRA SOC (and overall for any SOC) ([Figure 8](#), [Figure 9](#), [Figure 10](#), [Figure 11](#), [Figure 12](#)). These figures describe the number of subjects with an event (each subject counted once per SOC).

9.4. Deaths, Serious Adverse Events and other Significant Adverse Events

Individual data listings of deaths and serious AEs ([Table 15](#)) will be provided. The listing will include: subject ID, treatment, AE description, duration, reason reported as an SAE, severity, relationship to treatment,

alternate etiology if not related, action taken with study treatment, whether subject discontinued due to AE, outcome, MedDRA SOC, MedDRA HLG, and MedDRA PT.

9.5. Birth Control and Pregnancies

An individual data listing of pregnancy reports will be provided ([Listing 21](#), [Listing 22](#), [Listing 23](#), [Listing 24](#), [Listing 25](#)) if a pregnancy occurs post dosing.

Birth control method(s) will be listed for each subject with start date and end date ([Listing 26](#)).

9.6. Clinical Laboratory Evaluations

Toxicity grade criteria for laboratory results can be found in [Table 4](#).

Unplanned clinical laboratory evaluations will be listed, but excluded from tabular and graphical summaries, except when calculating the maximum severity post-baseline.

Screening and safety clinical laboratory results (chemistry, hematology, and urinalysis) will be listed ([Listing 9](#), [Listing 10](#), [Listing 11](#)). Additionally, abnormal laboratory results (graded mild, moderate, or severe) will be listed in [Table 17](#), [Table 18](#), and [Table 19](#). Measurements outside of the normal range, but not graded as mild, moderate, or severe, will be flagged as “ONR” (outside normal range) in the listings.

Laboratory results will be summarized in tables and figures:

- Tabularly, by parameter, treatment, time point, and toxicity grade (including maximum severity post-baseline)
 - Chemistry Parameters: [Table 20](#)
 - Hematology Parameters: [Table 22](#)
 - Urinalysis Parameters: [Table 24](#)
- Tabularly, by summary statistics for change from baseline, reported by parameter, treatment, and time point
 - Chemistry Parameters: [Table 21](#)
 - Hematology Parameters: [Table 23](#)
- Graphically, using box plots showing the change from baseline by parameter, treatment, and time point
 - Chemistry Parameters: [Figure 13](#), [Figure 14](#), [Figure 15](#), [Figure 16](#), [Figure 17](#), [Figure 18](#), [Figure 19](#), [Figure 20](#), [Figure 21](#), [Figure 22](#), [Figure 23](#), [Figure 24](#), [Figure 25](#), [Figure 26](#), [Figure 27](#), [Figure 28](#)
 - Hematology Parameters: [Figure 29](#), [Figure 30](#), [Figure 31](#), [Figure 32](#), [Figure 33](#), [Figure 34](#), [Figure 35](#), [Figure 36](#), [Figure 37](#), [Figure 38](#)

The following parameters will be presented (in order):

- Chemistry: Sodium, Potassium, Magnesium, Chloride, CO₂, Glucose (Fasting), BUN, Creatinine, Estimated GFR, Total Protein, Albumin, AST, ALT, AP, Total Bilirubin, and Direct Bilirubin
- Hematology: Hemoglobin, Hematocrit, Erythrocytes, Leukocytes; absolute counts of Neutrophils, Lymphocytes, Monocytes, Eosinophils, and Basophils; and Platelets

- Urinalysis: Glucose by Dipstick, Protein by Dipstick, Hemoglobin by Dipstick, Erythrocytes by Microscopic Evaluation, Leukocytes by Microscopic Evaluation, Bacteria by Microscopic Evaluation

Only laboratory parameters reported as continuous values will be included in tables of summary statistics for change from baseline and in box plots for change from baseline. Because microscopic urinalysis evaluation is only performed in subjects with an abnormal urine dipstick result, urinalysis parameters assessed by microscopic evaluation will be excluded from tables of summary statistics for change from baseline and in box plots for change from baseline. However, urinalysis parameters assessed by microscopic evaluation will be included in summaries of toxicity grading, where the toxicity grade will be imputed as “Normal” for subjects where microscopic evaluation was not performed.

Laboratory parameters that have grading criteria for both decreases (result lower than normal range and baseline measurement) and increases (result higher than normal range and baseline measurement) will be summarized separately by direction of change. For example, sodium will be summarized separately as “Sodium, Decrease” and “Sodium, Increase.”

In tables summarizing toxicity grading, maximum severity observed for the parameter after dosing and within the same dosing period will be summarized (max severity post-baseline). Results of maximum severity for “Any Parameter” will be included for chemistry, hematology, and urinalysis laboratory results. For “Any Parameter” results, the maximum severity across all laboratory parameters in the respective category is summarized by time point, and from maximum severity post baseline.

By protocol, up to one repeat of a planned clinical laboratory assessment is allowed (*Laboratory values that are outside the range of eligibility but are thought to be due to an acute condition or due to collection or laboratory error may be repeated once.*). If replicates for clinical laboratory results are present in the database, then only the second replicate will be summarized and reported. Replicates not used in the analysis will not be listed.

Viral serology screening results ([Listing 12](#)), urine toxicology and alcohol screening results ([Listing 13](#)), and serum hCG (Human Chorionic Gonadotropin) pregnancy test results ([Listing 14](#)) will be listed. If FSH is measured for any subject during the study, FSH will be included in [Listing 14](#).

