8.2.1 Clinical Laboratory Evaluations (Hematology, Chemistry, and Urinalysis)

Blood and urine samples for clinical laboratory tests will be collected at Screening Visit, on Day -1 of each dosing period (with the exception in the first dosing period if screening clinical labs were collected ≤7 days of Dose 1), on Day 2 of each dosing period, and Final Visit after Dose 4, or ET. Subjects must be fasting for > 4 h before any blood draw for clinical laboratory assessments. These tests will include:

- HEM: Hgb, Hct, RBC count, platelet count, and WBC count with absolute differential count
- CHEM: serum creatinine, with estimation of GFR, blood urea nitrogen (BUN), glucose (fasting at least 4 h), total bilirubin, direct bilirubin, alanine aminotransferase (ALT), aspartate aminotransferase (AST), alkaline phosphatase (AP), total protein, albumin, sodium, chloride, potassium, total carbon dioxide (CO₂), magnesium
- UA: Routine dipstick testing of clean-catch urine for blood, protein, and glucose; other coincidental tests will be recorded

Clinical laboratory tests at Screening Visit and Day -1 of Treatment Period 1 should be in the normal reference range with acceptable exceptions, as shown below and in [Appendix B](#):

Elevated bilirubin due to documented Gilbert syndrome that is Grade 1 is allowable, but Grade 2 or higher is exclusionary. [To document a subject has Gilbert syndrome, a diagnosis from the medical record must be provided or the PI may make a 'presumptive' diagnosis of Gilbert syndrome in subjects with unconjugated hyperbilirubinemia on repeated testing (at least two samples separated in time) who have otherwise normal serum ALT, AST, and AP concentrations, and a normal CBC.]

Elevated serum glucose, sodium, potassium, bicarbonate (CO₂), total protein, and AP values that reach toxicity Grade 1 values are allowable.

Serum chloride and albumin above the upper limit of normal (ULN) is allowable.

If UA by dipstick is not within acceptable ranges per [Appendix B](#) for blood, protein, or glucose, a complete UA with microscopic evaluation will be performed and the results will supersede those of the dipstick. Menstruating females failing inclusion criteria due to a positive urine dipstick or microscopic UA may be retested after cessation of menses. Do not exclude subjects with ≤ 6 RBC/HPF.

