11.4.5 Missing Values and Outliers

All attempts will be made to collect all data per protocol. No imputation will be performed for missing values. Outliers will not be excluded from the primary analyses. Outliers identified during the PK analysis will be discussed in the analysis report.

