4.5. Safety and PK Variables

The following section describes the safety and PK endpoints. Endpoints related to Holter ECG time points are described separately in the ECG SAP ([Appendix 4](#)). For a detailed schedule of procedures refer to [Table 2](#). Refer to Section 3 for a list of the primary and secondary objectives and outcomes.

Incidence, relatedness, and severity of treatment-emergent AEs and SAEs will be recorded from time of dose to Final Visit, or ET Visit.

The following other safety parameters will be assessed for each dosing period and at the Final Visit or ET Visit:

- Change from baseline in clinical safety laboratory parameters, as measured at the In-Patient Follow-up visit (the day after dosing), after a minimum 4 h fast.
 - Chemistry: Sodium, Potassium, Magnesium, Chloride, Total Carbon Dioxide (CO₂), Glucose (Fasting), Blood Urea Nitrogen (BUN), Creatinine, Estimated Glomerular Filtration Rate (GFR), Total Protein, Albumin, Aspartate Aminotransferase (AST), Alanine Aminotransferase (ALT), Alkaline Phosphatase (AP), Total Bilirubin, and Direct Bilirubin
 - Hematology: Hemoglobin, Hematocrit, Erythrocytes, Leukocytes, Neutrophils (absolute count), Lymphocytes (absolute count), Monocytes (absolute count), Eosinophils (absolute count), Basophils (absolute count), and Platelets
 - Urinalysis: Glucose by Dipstick, Protein by Dipstick, Hemoglobin by Dipstick. If dipstick testing is abnormal, a complete urinalysis with microscopic evaluation will be performed. Urinalysis microscopic evaluation parameters that will be graded and summarized may include Erythrocytes by Microscopic Evaluation, Leukocytes by Microscopic Evaluation, and Bacteria by Microscopic Evaluation.
- Change from baseline in vital signs parameters, as measured at 1 h (±10 minutes), 2 h (±10 minutes), 4 h (±10 minutes), and 24 h (±2 h) after dosing.
 - Systolic Blood Pressure, Diastolic Blood Pressure, Heart Rate, Respiratory Rate, and Temperature
- Change from baseline in 12-lead standard ECG with 10-sec rhythm strip parameters, as measured 1 h (±10 minutes), 2 h (±10 minutes), 4 h (±10 minutes) and 24 h (±2 h) after dosing.

-
- Overall interpretation of standard 12-lead ECGs (normal, abnormal not clinically significant [NCS], or abnormal clinically significant [CS]), and the following parameters: PR Interval; QRS Duration, QT Interval; QTcF Interval, RR Interval, ECG Mean Ventricular Rate

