6.5. Missing Data

No imputation of missing data is planned.

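### SAP 9.6 grades every unperformed urine microscopy as Normal, including a required test that was missed, and Table 24 does not show how many subjects were examined

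*SAP*

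**What the plan says.** SAP 9.6 lists three graded microscopy parameters: "Erythrocytes by Microscopic Evaluation, Leukocytes by Microscopic Evaluation, Bacteria by Microscopic Evaluation". It removes them from the change-from-baseline tables and box plots, and gives the reason: "Because microscopic urinalysis evaluation is only performed in subjects with an abnormal urine dipstick result". It keeps them in the toxicity-grade summaries, where the grade is imputed (the SAP's own verb) as Normal "for subjects where microscopic evaluation was not performed".

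The general rules point the other way. SAP 6.5 states: "No imputation of missing data is planned". Protocol 11.4.5 states: "No imputation will be performed for missing values". Neither names an exception for urinalysis.

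The screening step is defined in Protocol 8.2.1: "Routine dipstick testing of clean-catch urine for blood, protein, and glucose", with any incidental further tests recorded. SAP 4.5 makes microscopy a reflex test: "If dipstick testing is abnormal, a complete urinalysis with microscopic evaluation will be performed". SAP Table 24, the urinalysis grade table, reuses the Table 20 shell.

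**The concern.** A reflex test can be absent for two quite different reasons. It may not have been called for, or it may have been called for and missed. SAP 9.6 treats both alike. In the second case a safety test that the plan itself required, after a positive screen, is recorded as a normal finding.

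A second issue concerns what the screen measures. A clean blood dipstick is reasonable support for a normal red-cell grade. None of the three specified analytes is a test for white cells or bacteria, so for those two parameters a normal dipstick says little. A reader of the study report would see a row for urine leukocytes with a denominator and a low percentage, and would have no means of telling how many samples were looked at.

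**Working it through.** **Inputs.** The rule and its reason (SAP 9.6); the trigger (SAP 4.5, Protocol 8.2.1); the dipstick analytes (Protocol 8.2.1); the general missing-data rules (SAP 6.5, Protocol 11.4.5); the shell and footnotes of SAP Tables 20 and 24; 72 planned subjects (SAP 4.1). The plan states no abnormal-dipstick rate and no expected urinalysis rate, so there is no figure of its own to reproduce.

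**Step 1: whom the rule reaches.**

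| At the visit | Microscopy | Grade under SAP 9.6 | What supports it |
|---|---|---|---|
| Dipstick normal | Not required | Normal | Red cells: the blood dipstick. White cells, bacteria: no specified test |
| Dipstick abnormal | Done | As measured | The measurement |
| Dipstick abnormal | Required, missed | Normal | Nothing; the screen was positive |
| No dipstick | Not done | Normal, read literally | Nothing |

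The third and fourth rows are missing data in the ordinary sense, so they contradict SAP 6.5 and Protocol 11.4.5. The first row is absence by design.

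**Step 2: where the grade appears.** The Table 20 shell has N and Mild, Moderate and Severe columns, and no Normal column. Its footnote makes N the safety-population subjects with safety labs measured at that visit. An imputed Normal therefore never changes a count of graded subjects; it can act only by keeping the subject in N. On the plain reading of that footnote, a subject with labs but no microscopy is in N anyway. The shell, like the rule, leaves the number examined invisible.

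**Step 3: possible size, under assumptions.** Let f be the assumed chance that one post-dose dipstick is abnormal, with dipsticks treated as independent. There are two post-dose dipsticks per treatment (24 h and follow-up), hence eight over four treatments. The share never examined is 1 − f at one time point, (1 − f)² within a treatment and (1 − f)⁸ over the trial.

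| f | One time point | Within a treatment | All four treatments | Examined per time point (72f) |
|---|---|---|---|---|
| 2% | 98% | 96% | 85% | 1.4 |
| 5% | 95% | 90% | 66% | 3.6 |
| 10% | 90% | 81% | 43% | 7.2 |
| 20% | 80% | 64% | 17% | 14.4 |
| 30% | 70% | 49% | 6% | 21.6 |
| 50% | 50% | 25% | 0.4% | 36 |

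More than half are unexamined only if f is below 50% at a single time point, below 1 − 0.5^(1/2) = 29.3% for maximum severity within a treatment, and below 1 − 0.5^(1/8) = 8.3% for the row covering any period.

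Let q be the assumed share of examined samples with a graded white-cell result. With f = 10% and q = 30%, the tabulated rate is 0.10 × 0.30 = 3%, or 72 × 0.03 = 2.16 subjects. Among those examined it is 2.16/7.2 = 30%. The numerator is the same. If nothing is assumed about the other 90%, the rate for all subjects could logically lie anywhere from 3% to 3% + 90% = 93%.

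**Step 4: the missed test.** Suppose 2 of 72 are graded and one further subject's required microscopy was missed. The rate is 2/72 = 2.8% under SAP 9.6 and 2/71 = 2.8% with that subject removed. The percentage barely moves; what changes is that an unmeasured result is no longer treated as normal.

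**The case against.** The strongest reply is that a reflex test which was not triggered is not a missing value. Protocol 11.4.5 concerns data due under the protocol, and microscopy after a normal dipstick is not due. SAP 9.6 explains itself in the preceding sentence, so it can be read as a disclosed convention for one section. SAP 10.1 does the same for pharmacokinetics: it sets early concentrations below the quantification limit to zero and unrecorded sampling times to planned times. This stands. A reader might infer that every unperformed microscopy breaches the no-imputation rule, or that SAP 9.6 is its only exception. The documents support neither.

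It can also be said that a missed reflex test is not concealed. A dipstick of 1+ or more that is worse than baseline is graded in its own row, and a required procedure not done is a deviation shown in Table 5 and Listing 2. That also stands for the report as a whole, but it does not justify a Normal grade for a test that was required and not done.

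Finally, restricting N to subjects with microscopy would condition on a post-dose result and leave a small, selected group that may differ between treatments. That is a fair objection to a measured-only denominator, and a reason to display the number examined rather than replace N with it.

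**Conclusion.** The point holds in a limited form. The convention is wrong where microscopy was indicated but missed, or where no dipstick was done, because the grade is then missing and two general rules say it stays missing. For white cells and bacteria, Normal after a normal dipstick is unsupported by any specified test, and Table 24 does not disclose the number examined.

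A reader might go further and infer that the leukocyte and bacteria rates rest mostly on unmeasured results. That is plausible per visit in healthy volunteers screened on urinalysis, but no document gives an abnormal-dipstick rate, and it could easily fail for the any-period row. Nor is a known dilution of the percentages shown, given the visit-level N and the absence of a Normal column. All sizes above rest on assumed f and q and on independence.

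The consequence is confined to descriptive urinalysis percentages. Graded counts and the QTcF analysis are unaffected. This is a minor point that is cheap to repair.

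**What to change.** In SAP 9.6, apply Normal only when a dipstick was performed and did not call for microscopy. Where microscopy was indicated but not done, treat the grade as missing and take the subject out of N for that parameter.

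The rule needs one definition of the trigger. Protocol 8.2.1 refers to the acceptable ranges in Appendix B, which admit protein up to 1+ on investigator judgment. SAP 4.5 and Note 4 of Protocol Appendix C refer to an abnormal dipstick. These passages should be reconciled.

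For white cells and bacteria, keep the graded counts but add to Table 24 the number examined by microscopy and the number not performed, with a footnote stating the convention. In SAP 6.5, cross-refer to the specific rules in SAP 9.6 and 10.1.

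The cost is one SAP paragraph, one cross-reference, an extra column or footnote, and a slightly smaller N in some rows. No new data are needed.
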